**Open-Label Treatment with RBP-6000:**

On Day 1 of the study (first dose of RBP-6000), all subjects who meet enrollment criteria will receive a SC injection of 300 mg of buprenorphine in RBP-6000. Subsequent doses of RBP-6000 may be adjusted down to 100 mg and back up to 300 mg based on the medical judgment of the Investigator. After injection of RBP-6000, subjects will not be permitted to receive supplemental SUBOXONE sublingual film during the RBP-6000 treatment period. Subjects who require supplemental SUBOXONE sublingual film or other sublingual buprenorphine pharmacotherapy during the RBP-6000 treatment period will be withdrawn from the study and referred for appropriate treatment.

Subjects will return to the clinic for monthly injection visits (every 28 - 2/+ 4 days) for a total of up to 12 injections for *de novo* subjects or for a total of 6 injections for roll-over subjects. Electrocardiogram (ECG) recordings and vital signs will be collected pre and post each SC injection. Subject-reported injection site pain Visual Analog Scale scores (VAS) will be collected at various times for 1 hour after each injection. Local injection site grading will be collected at various time points starting immediately after injection; the injection site will be evaluated for pain, tenderness, warmth, itching, erythema, inflammation or swelling, and

bruising using a 4-point severity scale. At each visit after injections begin, the injection site will be assessed by site staff for potential reaction and will also be evaluated for evidence of attempts to remove the depot.

Subjects will return to the clinic weekly for the first 5 weeks and then biweekly (i.e., every 2 weeks) through to injection 6. After injection 6, visits will be monthly for the rest of the study period for urine drug screens (UDS), Timeline Followback (TLFB) interviews, opioid craving VAS evaluation, COWS and subject reported outcomes (Subjective Opiate Withdrawal Scale [SOWS]). Subjects will continue to receive counseling (manual-guided behavioral therapy) during the study.

Safety assessments will be collected at each injection visit and/or at injection follow-up visits and will include the following: vital signs, electronic Columbia Suicide Severity Rating Scale (eC-SSRS) responses, ECGs, laboratory tests (hematology, chemistry, urinalysis, and pregnancy test), use of concomitant medications, and the frequency of AEs.

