On Day 1 of the study (initiation of study drug injections), all subjects will receive a SC injection of 300 mg of buprenorphine in RBP-6000. Subsequent doses of RBP-6000 may be adjusted down to 100 mg and back up to 300 mg based on the medical judgment of the Investigator. After injection of RBP-6000, subjects will not be permitted to receive supplemental SUBOXONE sublingual film during the RBP-6000 treatment period. Subjects who require supplemental SUBOXONE sublingual film or other sublingual buprenorphine pharmacotherapy during the RBP-6000 treatment period will be withdrawn from the study and referred for appropriate treatment.

Subjects will return to the clinic for monthly injection visits (every 28 - 2/+ 4 days) for a total of up to 12 injections for *de novo* subjects or for a total of 6 injections for roll-over subjects. ECG recordings and vital signs will be collected pre and post each SC injection. All ECGs will be interpreted by a central monitoring facility. Subject-reported injection site pain Visual Analog

Scale scores (VAS) will be collected at various times up to 1 hour after each injection. Local injection site grading will be collected at various time points starting immediately after injection and will be evaluated for pain, tenderness, warmth, itching, erythema, inflammation or swelling, and bruising using a 4-point severity scale. At each visit after injections begin, the injection site will be assessed by site staff and will also be evaluated for evidence of attempts to remove the depot.

Subjects will need to return to the clinic weekly for the first 5 weeks and biweekly (i.e., every 2 weeks) until injection 6, and monthly for the rest of the study period for urine drug screens (UDS), Timeline Followback (TLFB) interviews, opioid craving VAS evaluation, COWS and subject reported outcomes (Subjective Opiate Withdrawal Scale [SOWS]). Subjects will continue to receive counseling (manual-guided behavioral therapy) during the study.

Safety assessments will be collected at each visit and will include the following: vital signs, electronic Columbia Suicide Severity Rating Scale (eC-SSRS) responses, ECGs, laboratory tests (hematology, chemistry, urinalysis, and pregnancy test), concomitant medications, and AEs.

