### 6.11.1 Timeline Followback Interview

The TLFB Interview will be administered according to the SOE in [Appendix 1](#), [Appendix 2](#), [Appendix 3](#), [Appendix 4](#), and [Appendix 5](#). The TLFB Interview is a method to assess recent drug use and will be administered electronically. The questionnaire should be administered by an interviewer. The interview instrument asks subjects to retrospectively estimate their drug use in the 30 days prior to screen at the screening visit and since the last visit at all subsequent visits. Only occurrence of use is captured (i.e., used or did not use) (Fals-Stewart 2000). The interview takes approximately 10-30 minutes to complete and is appropriate for males and females 14 years of age and older. Drugs to be assessed in this study include opioids, methadone, buprenorphine, cocaine, barbiturates, benzodiazepines, amphetamines/methamphetamine, phencyclidine, and ethanol ([Appendix 17](#)).

The timeline followback interview should be completed prior to SUBOXONE and RBP-6000 injection and at approximately the same time each day  $\pm$  2 hours.

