**Appendix 17 Timeline Followback (TLFB) Interview**

TIMELINE FOLLOWBACK INTERVIEW											Ethanol
Study Day	Date (mm / dd / yyyy)	Opioids	Methadone	Bup	Cocaine	Barbit.	Benzos	Amp/Meth	PCP	Completed By: (initials/date)	
	□□ / □□ / 20□□	 Use  No Use	_____	 Use  No Use							
	□□ / □□ / 20□□	 Use  No Use	_____	 Use  No Use							
	□□ / □□ / 20□□	 Use  No Use	_____	 Use  No Use							
	□□ / □□ / 20□□	 Use  No Use	_____	 Use  No Use							
	□□ / □□ / 20□□	 Use  No Use	_____	 Use  No Use							
	□□ / □□ / 20□□	 Use  No Use	_____	 Use  No Use							
	□□ / □□ / 20□□	 Use  No Use	_____	 Use  No Use							
	□□ / □□ / 20□□	 Use  No Use	_____	 Use  No Use							
	□□ / □□ / 20□□	 Use  No Use	_____	 Use  No Use							

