The suicidal ideation intensity rating is the sum of the five intensity item scores to create a total score (range 0 to 25). The five intensity items include frequency, duration, controllability, deterrents, and reason for ideation. Each item is scored from 0 to 5 with 5 representing the most severe intensity.

Suicidal Behavior Scoring

The suicidal ideation score ranges from 0 to 5 and depends on the answers to the suicidal behavior portion of the eC-SSRS. The score is the maximum suicidal ideation category (in the following order: 1 = preparatory acts or behavior, 2 = aborted attempt, 3 = interrupted attempt, 4 = actual attempt, and 5 if the subject has an AE with a preferred term of completed suicide. If all answers to these questions are "No" and the subject does not have an AE with a preferred term of completed suicide then the suicidal behavior score is 0.

Treatment Duration (weeks)

Treatment duration will be defined as $(\text{treatment stop date} - \text{treatment start date} + 1)/7$ where treatment stop date is defined as date of last RBP-6000 injection + 28 days.

Sponsor: Indivior Inc.
 Protocol no: RB-US-13-0003

Percentage of Urine Drug Screen and Self-Report Results

Subjects' self-reported illicit drug use from the TLFB and results from the UDS will be combined into a single endpoint in the following manner:

- If both the TLFB and the UDS have a negative result at a particular visit, then the visit will be considered to have a negative result at that visit.
- If either the TLFB or UDS, or both, have a non-negative result at a particular visit, then the visit will be considered to have a non-negative result at that visit.
- To be conservative, missing UDS or TLFB data will be imputed as non-negative.

Urine Drug Screen Result for Opioids	Self-Report of Illicit Opioid Use Result	Overall Result
Nonnegative	Nonnegative	Nonnegative
Nonnegative	Negative	Nonnegative
Negative	Nonnegative	Nonnegative
Negative	Negative	Negative

Treatment Success

A subject is defined as a treatment success if $\geq 80\%$ urine samples negative combined with self-reports negative.

Visit Window for Remapping of Early Termination visit

Duration will be derived in days as (ET visit date – treatment start date) + 1.

Sponsor: Indivior Inc.
 Protocol no: RB-US-13-0003

Visit window for safety and efficacy assessments.

Study Visit	Lower Window for Analysis Day (ADY)	Upper Window for ADY
Week 1 Day 1	1	1
Week 1 Day 2	2	5
Week 2 Day 8	6	12
Week 3 Day 15	13	19

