use, as defined in [Section 5](#); for example, 10% on the x-axis represents the proportion of subjects who had at least 10% of their self-reported opioid drug use combined with UDS as abstinent.

Additionally, a table showing the percentage of subjects with negative results at each visit will be provided.

All missing results for opioids were considered nonnegative for opioids. Opioids non-negative indicates detection of buprenorphine (only self-reports), codeine, hydrocodone, hydromorphone, methadone, morphine, opiates, oxycodone, and oxymorphone in the urine drug screen and reporting of amphetamine/methadone, buprenorphine, methadone, and opioids use in the timeline followback.

The number and percentage of subjects abstinent between visits will be summarized by subject type for the Safety Analysis Set. Additionally, the time to first urine sample non-negative or TLFB self-report of non-negative for opioids will be analyzed in the Safety Analysis Set for subjects who are Abstinent on Day 1 using Kaplan-Meier analysis methods to determine the first quartile (25%) and median (days) along with their corresponding confidence intervals in each subject type and overall. Subjects who are abstinent throughout the trial will be censored on the date of their last negative urine sample of TLFB self-report for opioids.

The number and percentage of subjects who have a non-negative result in each substance tested in the UDS will be reported by subject type in the Safety Analysis Set. Additionally, the number and percentage of subjects at each visit who tested non-negative for non-opioid substances will be summarized by subject type in the Safety Analysis Set in a tables and in figures for amphetamine, barbiturates, benzodiazepine, cannabinoids, and phencyclidine.

Opioid TLFB and UDS results will be listed together. Additionally, all drugs identified in the TLFB interviews and detected in the UDS will be listed separately for the Safety Analysis Set.

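### The TLFB part of the opioid composite looks back 7, then 14, then 28 days, so by-visit abstinence and the summaries pooled over visits partly reflect the visit schedule

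*SAP*

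**What the plan says.** Protocol 6.11.1 has subjects "retrospectively estimate their drug use in the 30 days prior to screen at the screening visit and since the last visit at all subsequent visits". Protocol 3.1 sets the visits "weekly for the first 5 weeks and biweekly (i.e., every 2 weeks) until injection 6, and monthly for the rest of the study period".

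SAP 5.0 merges TLFB and urine screen into one result per visit. A visit is negative only when both are negative; the other branch begins "If either the TLFB or UDS, or both, have a non-negative result at a particular visit". Neither this rule nor the SAP 5.0 definition of abstinence gives a time window, and the SAP does not say how several days of TLFB entries become one visit result.

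SAP 9.5.1 uses the visit result in several ways: percent-negative categories with a continuous summary, a CDF of percent abstinence, and a by-visit table ("Additionally, a table showing the percentage of subjects with negative results at each visit will be provided"). SAP 5.0 adds a treatment-success rule at 80% or more negative. SAP 9.0 presents summaries by subject type by default and shows visits that do not apply to roll-over subjects as N/A. None of these outputs is adjusted for the length of the interval covered.

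**The concern.** The natural reading of Protocol 6.11.1 with SAP 5.0 is that a visit's TLFB component is non-negative if any opioid use is reported since the previous visit. An any-use indicator over 28 days is not the same measurement as one over 7 days: a subject who uses occasionally at a constant rate has four times as many days in which to turn the visit non-negative.

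Two readings of the results are at stake. The first is the trend over time. The look-back lengthens at Day 43 and at Day 169, the first visit after the sixth injection interval, and in a long-term study a drop there invites the interpretation that effect is being lost. The second is the comparison of subject types in summaries that pool all of a subject's visits, because de novo subjects contribute many more 28-day visits.

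**Working it through.** The documents state no abstinence rate, so there is no figure of the plan's own to reproduce. The schedule is fixed by the documents; the use rates are assumptions.

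**Step 1: look-backs.** TLFB days after Day 1, from the schedules of events (Protocol Appendices 2 to 5), are 8, 15, 22, 29, then every 14 days from 43 to 141, then every 28 days from 169 to 337. Roll-over subjects stop at Day 169.

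| | 7 days | 14 days | 28 days | Visits | Mean look-back |
|---|---|---|---|---|---|
| Roll-over | 4 | 8 | 1 | 13 | 168/13 = 12.9 days |
| De novo | 4 | 8 | 7 | 19 | 336/19 = 17.7 days |

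The share of 28-day visits is 1/13 = 8% against 7/19 = 37%. Up to and including Day 169 the two types have the same look-back at every visit.

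**Step 2: equal-risk subjects.** Assume a constant, independent daily probability of use p, fully reported, TLFB component only. Then P(visit negative) = (1 − p)^L with L = 7, 14 or 28. The pooled mean weights these by the visit counts above. At p = 2%:

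- 0.98^7 = 86.8%, 0.98^14 = 75.4%, 0.98^28 = 56.8%.
- Roll-over: (4 × 86.8 + 8 × 75.4 + 1 × 56.8)/13 = 77.5%.
- De novo: (4 × 86.8 + 8 × 75.4 + 7 × 56.8)/19 = 70.9%.

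| p per day | 7 / 14 / 28 days, % negative | Pooled roll-over v de novo | Gap, points |
|---|---|---|---|
| 0.25% | 98.3 / 96.6 / 93.2 | 96.8 v 95.7 | 1.1 |
| 1% | 93.2 / 86.9 / 75.5 | 87.9 v 84.0 | 3.9 |
| 2% | 86.8 / 75.4 / 56.8 | 77.5 v 70.9 | about 6.5 |
| 5% | 69.8 / 48.8 / 23.8 | 53.3 v 44.0 | 9.3 |

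**Step 3: more realistic populations.** A simulation of 20,000 subjects with unchanging behaviour added a 3-day urine window (assumed) and let subjects differ strongly, most being near-abstinent or frequent users. No dropout was modelled.

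| Mean daily use, spell length, reporting | Days 8–29 | Days 169–337 | Fall | Pooled roll-over v de novo | Gap |
|---|---|---|---|---|---|
| 5%, 1 day, full | 87.7 | 82.2 | 5.5 | 85.6 v 84.5 | 1.1 |
| 5%, 5 days, full | 92.0 | 88.0 | 4.0 | 90.5 v 89.7 | 0.8 |
| 20%, 1 day, full | 66.1 | 57.7 | 8.4 | 62.7 v 61.1 | 1.6 |
| 20%, 5 days, full | 72.5 | 65.6 | 6.9 | 70.0 v 68.6 | 1.4 |
| 20%, 14 days, full | 76.3 | 71.1 | 5.2 | 74.5 v 73.5 | 1.0 |
| 20%, 5 days, 50% | 74.9 | 71.4 | 3.5 | 73.6 v 72.9 | 0.7 |
| 20%, 5 days, none | 76.3 | 76.3 | 0 | 76.4 v 76.4 | 0 |

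The 80% success rule behaves likewise. With equal-risk subjects at 2% it is met by 41.0% of roll-over and 14.4% of de novo subjects. In the five fully reported mixed populations the difference is 1.1 to 2.2 points.

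**Step 4: check of the cause.** With a fixed 7-day look-back in the same simulations, the by-visit series is flat and the pooled means agree (86.8 v 86.8 at 2%; 72.5 v 72.5 in the 20%, 5-day mixed population). The lengthening look-back is therefore what produces the pattern.

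**The case against.** The best defence has four parts.

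- **Limited consequence.** These are secondary, descriptive outcomes of an open-label safety study, with no test across visits or between subject types. The SAP also provides urine results by substance, a Kaplan-Meier time to first non-negative result, and listings. This limits the consequence. It does not remove it, because a descriptive trend is exactly what readers will interpret.
- **Unwritten rule.** The any-use-since-last-visit rule appears nowhere in the SAP, and the table shells are in a separate document not available here. This stands: the rule is an inference. If another rule is intended, the SAP still needs to state it.
- **Size depends on behaviour.** There is no effect for subjects who never use, for daily users, or where urine alone decides the result. This stands, and is why only a range can be given.
- **A short window has its own cost.** Seven days before each visit covers 13 × 7 = 91 of 168 days for roll-over (54%) and 19 × 7 = 133 of 336 for de novo (40%). After Day 141 it ignores 21 of every 28 days. A subject with negative urine who reports use 10 days before each monthly visit would count as negative every time, contrary to the SAP's conservative intent. This stands against making such a composite the main measure.

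A reader might infer that de novo subjects look worse than roll-over subjects in the by-visit table. They do not for this reason: look-backs are identical at every shared visit, and later roll-over cells are N/A. Nor can any observed decline after injection 6 be put down to the look-back. Real change, and missing results counted as non-negative, could also lower the percentages. The Kaplan-Meier estimate is dated more coarsely by longer intervals but is not inflated by them.

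**Conclusion.** The point holds in a limited form. The documents fix the lengthening look-back, the both-negative rule and the absence of any interval adjustment. Given the natural reading of the visit rule, the direction follows for intermittent users who report their use: percent negative falls at Day 43 and Day 169 with no change in behaviour, and pooled percent negative, the CDF and 80% success are lowered for de novo relative to roll-over.

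The documents do not fix the size. Equal-risk subjects at 0.25% to 5% daily use give a pooled gap of about 1 to 9 points. Strongly mixed populations with full reporting give a by-visit fall of about 4 to 8 points and a pooled gap of about 1 to 1.6 points. With half of use reported these are 3.5 and 0.7, and with none they are zero. The mixed figures rest on the assumed spell lengths and urine window, and all figures assume constant behaviour and no dropout. The step pattern starts at Day 8; Day 1 has a separate look-back reaching to screening.

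**What to change.** First confirm that the ePRO captured use by calendar date, as the form in Protocol Appendix 17 is laid out. SAP 9.5.1 records that the tablet departed from the planned interview on one drug question, so the form alone is not proof. Then, in SAP 5.0 and 9.5.1:

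1. State how daily TLFB entries become a visit result, and keep the conservative since-last-visit composite.
2. Add percent of TLFB days without opioid use, by visit interval and overall, as the measure for reading trends over time. It does not depend on visit spacing and discards no reported use.
3. Compare subject types on pooled percent negative, the CDF and 80% success over Day 1 to 169 only, and show full-period de novo results separately.
4. Present a composite with a fixed 7-day TLFB look-back as a sensitivity analysis, not as the main measure.

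The cost is SAP wording, one extra derivation and some added tables. If use was captured by date, no new data are needed.

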9.5.2 Clinical Opioid Withdrawal Scale (COWS) Total Score

COWS total scores will be summarized by clinical visit and subject type using descriptive statistics (mean, median, SD, minimum, and maximum), including change from baseline. A listing of the COWS assessment will be provided for the Safety Analysis Set. Additionally, separate listings for the actual values (individual responses and total scores) and the change from baseline in total COWS score will be presented for the Safety Analysis Set.

A figure for the COWS scores over time will be created for all subjects in the Safety Analysis Set. An additional table and figure will be created for the Safety Analysis Set excluding subjects using illicit opioids (either by UDS or TLFB) at any time during the study.

9.5.3 Subjective Opioid Withdrawal Scale (SOWS) Total Score

SOWS total scores will be summarized using descriptive statistics (mean, median, SD, minimum, and maximum), including change from baseline. A listing of the SOWS assessment will be provided for the Safety Analysis Set. Additionally, separate listings for the actual values (individual responses and total scores) and the change from baseline in total SOWS score will be presented for the Safety Analysis Set.

A figure for the SOWS scores over time will be created for all subjects in the Safety Analysis Set. An additional table and figure will be created for the Safety Analysis Set excluding subjects using illicit opioids (either by UDS or TLFB) at any time during the study.

9.5.4 Opioid Craving VAS Total Score

Opioid Craving VAS total scores will be summarized using descriptive statistics (mean, median, SD, minimum, and maximum), including change from baseline for the Safety Analysis Set. Additionally, separate listings for the actual values and the change from baseline in opioid craving VAS total scores will be presented for the Safety Analysis Set.

Sponsor: Indivior Inc.
Protocol no: RB-US-13-0003

A figure for the Opioid Craving VAS scores over time will be created for all subjects in the Safety Analysis Set. An additional table and figure will be created for the Safety Analysis Set excluding subjects using illicit opioids (either by UDS or TLFB) at any time during the study.

9.6 Primary Safety Analyses

9.6.1 Incidence of Adverse Events

9.6.1.1 Adverse Events

Imputation of AE (for determination of TEAE only) and concomitant medication start and stop dates:

Start Date: If only 'day' is missing, and the month and year are not the same as the month of first dose, then impute day with '01'. Otherwise, if the month and year are the same as the first dose date, use the first dose date. If 'day' and 'month' are missing, and 'year' is not missing, then impute month and day with month and day of the first dose date (assuming same 'year'). If 'day' and 'month' are missing and 'year' is not missing and is not the same year as first dose date, then impute with '01' for both 'day' and 'month'. If the start date is completely missing, it will be set to the first dose date.

Stop Date: If only 'day' is missing, impute day with last day of the month. If 'day' and 'month' are missing, and 'year' is not missing, then impute month with '12' and day with '31' (or date of study discontinuation/completion if earlier than 12-31 and year is the same as the year of discontinuation). If the stop date is completely missing, it will be set to the date of study discontinuation/completion. A stop date will not be applied to ongoing AEs or ongoing medications.

Treatment-related Adverse Events

Any AE with a relationship to study treatment of 'Related' or missing will be considered a treatment-related AE as determined by the Investigator.

A summary of treatment-emergent AEs will be presented for the Safety Analysis Set and the Run-In Safety Analysis Set, including the number of events reported, the number and percentage of subjects reporting at least one AE, the number and percentage of subjects with the following:

- Related AEs
- SAEs
- Related SAEs
- AEs with an outcome of death
- Severe TEAEs
- AEs leading to discontinuation

A breakdown of the number and percentage of subjects reporting each AE categorized by SOC and PT coded according to the MedDRA dictionary version 17.1 will be presented for the Run-In period using the Run-In Safety Analysis Set and for the open label RBP-6000 treatment period using the Safety Analysis Set. Note that counting will be by subject not event and subjects are only counted once within each SOC or PT. AEs/TEAEs related to SUBOXONE/study treatment will be presented in a similar manner.

A further tabulation of events experienced by $\geq 5\%$ of subjects by SOC and PT will be presented for the Safety Analysis Set.

A summary of events reported, categorized by severity, will also be provided. Subjects with multiple events within a particular SOC or PT will be counted under the category of their most severe event within that SOC or PT. A further tabulation of severe AE/TEAEs will be presented by SOC and PT.

Additionally, treatment-related AEs/TEAEs will be summarized by maximum severity (Mild, Moderate, or Severe). A breakdown of severe treatment-related AEs/TEAEs by SOC and PT will be provided.

All AEs (including non-TEAEs) recorded on the CRF will be listed.

Sponsor: Indivior Inc.
Protocol no: RB-US-13-0003

